### A3.Partial/Missing Date Convention

In all listings, missing or incomplete dates should be left as they have been recorded. However, for calculation / sorting / assignation based on dates, the following methods will be used:

- The most conservative approach will be systematically considered (i.e. if the onset date of an AE/concomitant medication is missing / partial, it is assumed to have occurred during the study treatment phase (i.e. a TEAE for AEs) except if the partial onset date or the stop date indicates differently).
- Where this is possible, the derivations based on a partial date will be presented as superior inequalities (i.e.: for an AE started in FEB2004 after the first IMP administration performed on 31JAN2004, the days since last dose will be “ $\geq 2$ ”, similarly the duration of ongoing AEs or medication will be “ $\geq xx$ ” according to the start and last visit dates).

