Mucocutaneous effects	Mucocutaneous toxicities are the most common side effects of systemic retinoids and are generally treatable, dose-dependent, and reversible. The most frequently reported AEs during FOP clinical studies with palovarotene were primarily mucocutaneous in nature, including cheilitis/dry lips, dry skin, pruritus and alopecia, and were generally assessed as related to palovarotene.	
Participant selection: Participants who were intolerant to prior treatment with palovarotene will not be included in the study (Section 5.2).
 
Instruction: Participants will be instructed to utilise symptomatic therapy (e.g. analgesics, skin emollients, lip moisturisers, artificial tears, or other helpful treatments), to minimize these side effects, or as prophylaxis in the study.
 
Participant monitoring: During the study, participants will be monitored for signs of mucocutaneous effects and any events will be recorded as AEs (Section 8.3).
 
Study intervention withdrawal criteria: The daily dose of palovarotene can be reduced for any intolerable adverse effects. If already receiving the lowest dose, palovarotene can be temporarily or permanently discontinued or the participant switched to flare-up treatment only (Section 6.5).

Photosensitivity	Photosensitivity reactions, such as exaggerated sunburn reactions (e.g. burning, erythema, blistering) involving areas exposed to the sun have been associated with the use of retinoids. Although palovarotene has not been proven to be phototoxic, precautionary measures for phototoxicity are recommended.	
Participant selection: Participants who were intolerant to prior treatment with palovarotene, or any other medical condition that would expose the participant to undue risk, will not be included in the study (Section 5.2).
 
Instructions: Participants should avoid excessive exposure to sun and use protection from sunlight when it cannot be avoided (use of sunscreens, protective clothing, and use of sunglasses).
 
Participant monitoring: During the study, participants will be monitored for signs of photosensitivity and any events will be recorded as AEs (Section 8.3).

Potential Risk of Clinical Significance	Summary of Data/Rationale for Risk	Mitigation Strategy

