- A summary of the number and percentage of participants reporting a non-Serious TEAE by SOC and PT
- A summary of the number and percentage of participants reporting a non-Serious related TEAE by SOC and PT
- A summary of the number and percentage of participants reporting a TEAE leading to treatment discontinuation by SOC and PT
- A summary of the number and percentage of participants reporting a TEAE leading to dose change (increase or decrease) by SOC and PT

The below summaries will also be provided by treatment dose at time of AE onset (5mg, 10/20mg and all palovarotene):

- Overall summary of Adverse events
- A summary of the number and percentage of participants reporting a TEAE by SOC and PT

- A summary of the number and percentage of participants reporting a TEAE by maximum intensity, SOC and PT
- A summary of the number and percentage of participants reporting a TEAE by worst causality, SOC and PT
- A summary of the number and percentage of participants reporting a TEAE leading to treatment discontinuation by SOC and PT
- A summary of the number and percentage of participants reporting a TEAE leading to dose change (increase or decrease) by SOC and PT

To calculate the treatment regimen at time of AE onset, the start date of each AE will be merged with each participant dosing log. Given dosing end dates are not captured the latest dosing record prior to the AE start date will be identified. If the dosing record is either 0 mg or after treatment discontinuation the regimen will be set to “off treatment”.

AEs will be counted as follows:

- AEs summaries will be ordered in terms of decreasing frequency for SOC and PT within the overall column of each output.
- Participants with more than one AE within a particular SOC are counted only once for that SOC. Similarly, participants with more than one AE within a particular PT are counted only once for that PT.
- Participants reporting a TEAE more than once within that SOC/ PT, the TEAE with the worst-case intensity (intensity order: severe > missing > moderate > mild) will be used in the corresponding intensity summaries.
- Participants reporting a TEAE more than once within that SOC/ PT, the TEAE with the worst-case causality to study medication (order: related > missing > not related) will be used in the corresponding relationship summaries;

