#### *Algorithm for TEAE*

The date imputation algorithm for incomplete adverse event start dates is described in the table below. Classification of adverse event according to its treatment-emergent status is then done using the imputed date.

In the following table, all dates are presented using an YYYY-MM-DD format. As an example, suppose First IMP administration = 2002-08-11 and several AEs have incomplete start dates.

Description of incomplete date	Imputed numeric date	Example	
		Character date	Imputed date
Day is missing			
YYYY-MM < YYYY-MM of [First IMP admin.]	YYYY-MM-01	2002-07-XX	2002-07-01
YYYY-MM = YYYY-MM of [First IMP admin.]	Min ([First IMP admin.], AE end date)	2002-08-XX	Min (2002-08-11, AE end date)
YYYY-MM > YYYY-MM of [First IMP admin.]	YYYY-MM-01	2002-09-XX	2002-09-01
Day and month are missing			
YYYY < YYYY OF [First IMP admin.]	YYYY-01-01	2001-XX-XX	2001-01-01
YYYY = YYYY OF [First IMP admin.]	Min ([First IMP admin.], AE end date)	2002-XX-XX	Min (2002-08-11, AE end date)

YYYY > YYYY OF [First IMP admin.]	YYYY-01-01	2003-XX-XX	2003-01-01
Day, month, and year are missing			
XXXX-XX-XX	Min ([First IMP admin.], AE end date)		Min (2002-08-11, AE end date)

YYYY = non-missing year, MM = non-missing month, DD = non-missing day, XX = missing field.

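### The SAP gives no rule for dose at AE onset when the AE start date is partial, and its only AE date imputation would misplace events around flare-up dose changes in both directions

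*SAP*

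**What the plan says.** **Dose at onset (SAP 5.7.2.2).** Six AE summaries are repeated by dose at onset, in columns for 5 mg, 10/20 mg and all palovarotene. The deaths and SAEs section adds a seventh, for serious TEAEs. The method is that "the start date of each AE will be merged with each participant dosing log", taking the most recent dosing record before the AE. There is a category for events off treatment, but none for events whose dose cannot be determined. The section does not say whether a recorded or an imputed date enters the merge.

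**Partial dates (SAP Appendix A3).** The lead-in states that "for calculation / sorting / assignation based on dates, the following methods will be used". The general principle is to be conservative: where an AE onset date is incomplete, "it is assumed to have occurred during the study treatment phase (i.e. a TEAE for AEs" unless the partial date or the stop date shows otherwise. A separate table, headed as the algorithm for TEAE, gives the imputed dates. Its one stated use is: "Classification of adverse event according to its treatment-emergent status is then done using the imputed date". For a month after the first-dose month, the row reads "YYYY-MM > YYYY-MM of [First IMP admin.] YYYY-MM-01 2002-09-XX 2002-09-01". For a year after the first-dose year with month and day missing, it imputes 1 January. In the month of first dosing the row is different: "YYYY-MM = YYYY-MM of [First IMP admin.] Min ([First IMP admin.], AE end date"). The same minimum applies to year-only dates in the year of first dosing and to fully missing dates.

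**Study day (SAP 5.1.4).** Study day stays missing when the event date is partial, while durations use the A3 imputations.

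**The concern.** An early date is a safe choice for treatment-emergent status, because any date after first dosing gives the same answer. It is not neutral for dose. A flare-up course can start on any day of a month, and the 1st of that month usually precedes it. An AE that begins a few days after the increase and is recorded only by month would then be matched to the chronic dose. The same rule works in reverse at the end of a course: an AE that begins after the return to chronic dosing, recorded only by month, is dated back into the course.

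At stake are the seven dose-at-onset tables. The treatment-regimen groups classify participants, so the AEs of someone who had both chronic and flare-up treatment are pooled across doses. The dose-at-onset tables are the planned summaries that compare doses at event level. The question is relevant here. Protocol 2.2.3 reports that mucocutaneous AEs leading to dose reduction were more common on the 20/10 mg flare-up treatment than on chronic treatment. Table 2 of the protocol calls such toxicities of systemic retinoids "generally treatable, dose-dependent, and reversible". Events close to a dose change carry much of the information on that question, and they are the ones the rule can misplace.

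**Working it through.** **1. Reproduce the plan's own examples.** With first dosing on 2002-08-11, the A3 table as written gives:

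| Recorded | Imputed |
|---|---|
| 2002-07-XX | 2002-07-01 |
| 2002-08-XX | 2002-08-11, or the AE end date if earlier |
| 2002-09-XX | 2002-09-01 |
| 2001-XX-XX | 2001-01-01 |
| 2002-XX-XX | 2002-08-11, or the AE end date if earlier |
| 2003-XX-XX | 2003-01-01 |
| fully missing | 2002-08-11, or the AE end date if earlier |

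All of these agree with the SAP.

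**2. One illustrative course.** First dosing is 10 January 2022. A flare-up course starts on 20 June 2022 and lasts 84 days (28 + 56, protocol 6.1), so it ends on 11 September 2022. Only the day is missing.

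| True onset | Dose in force | Imputed | Dose assigned |
|---|---|---|---|
| 24 June | flare-up | 1 June | chronic |
| 12 July | flare-up | 1 July | flare-up |
| 15 September | chronic | 1 September | flare-up |

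The first row loses a flare-up event and the third gains a chronic one.

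**3. Average share, day missing.** Assume a 30-day month, a course starting on day d (each of 1 to 30 equally likely) after the first-dose month, and onset uniform over the window. A dosing record dated on the imputed day counts as in force. For d = 1 nothing moves. For d ≥ 2, the course days left in the starting month are imputed to before the course.

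- Whole course: the sum of (31 − d) over d = 2 to 30 is 435; 435/30 = 14.5 days; 14.5/84 = 17.3%.
- First 28 days: the sum of min(28, 31 − d) over d = 2 to 30 is 434; 434/30 = 14.5 days; 14.5/28 = 51.7%.
- After the course: if it ends on day e, the remaining 30 − e days of that month are imputed to the 1st, which lies inside the course. The sum over e = 1 to 30 is 435, again 14.5 days, or 17.3% of the next 84 days.

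**4. Check on the real calendar.** Enumerating 730 consecutive start dates, none in the first-dose month:

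| Window, day missing | In course, moved to chronic | After course, moved to flare-up |
|---|---|---|
| 7 days | 87% | 87% |
| 14 days | 75% | 75% |
| 28 days | 52% | 52% |
| 84 days | 17.6% | 17.6% |

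With month and day both missing, in a year after first dosing, 88% of in-course AEs leave the course and 23% of those in the following 84 days enter it.

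**5. Effect on a planned column.** The tables pool 10 mg and 20 mg, so the 84-day share is the relevant one. The documents give no rate of partial AE dates. Assuming 5% to 15%, all with only the day missing: 0.05 × 17.3% = 0.9% and 0.15 × 17.3% = 2.6% of 10/20 mg AEs leave that column, before inflow from the period after a course.

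**The case against.** The strongest objection is about scope. The AE table is headed as a TEAE algorithm and names only treatment-emergent status as its use. The broad lead-in sits above general bullets, one of which prefers inequalities to single dates where possible. SAP 5.1.4 leaves study day missing, so imputed dates do not feed everything. A reader might infer that the SAP prescribes the A3 date for dose assignment; it does not say so. This part of the objection stands. It does not close the gap, because the merge needs a date, no other AE start-date rule exists, and no exception is written for dose at onset as one is for study day. On the narrow reading, the choice is left to programming.

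Four further points stand in part:

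- A reader might infer that events move only toward the lower dose. The calculation shows similar proportions moving each way when only the day is missing. Net counts would shift toward chronic dosing only if AEs were more frequent in the course than after it.
- A reader might take the 52% as the effect on a table. There is no 20 mg column, and the share applies only to day-missing AEs in the first 28 days of a course.
- Flare-up treatment starts after contact with the investigator, and participants must report intolerable reactions at once (protocol 6.1 and 6.5). Partial dates may therefore be less common around dose increases than six-monthly visits suggest.
- Listings keep dates as recorded, so affected events can be found, and the regimen-group tables give some participant-level information on dose.

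The sentence on dose-dependence in protocol Table 2 concerns systemic retinoids as a class, so it supports the relevance of the question and is not a palovarotene result. Likewise, A3 claims to be conservative only for on-treatment status, not for dose.

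**Conclusion.** The point holds as a gap with a predictable consequence. The SAP does not say which date determines dose at onset when the AE date is partial. If the only AE imputation in the plan is used, events near dose changes are misassigned in both directions, which blurs the 5 mg versus 10/20 mg comparison.

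The size is modest: about 17% of day-missing AEs in an 84-day course leave it, a similar share of those in the next 84 days enter, and about 0.9-2.6% of 10/20 mg AEs leave the column before inflow if 5-15% of dates are partial. These figures assume uniform onset, one isolated course after the first-dose month, and only the day missing. The 5-15% is an assumption without a source in the documents.

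The documents do not support a claim that A3 always imputes the earliest possible date. In the month or year of first dosing, and for fully missing dates, it uses the earlier of first dosing and AE end date. AEs with complete dates are unaffected, the analyses are descriptive, and overall TEAE incidence does not change. Severity is low, and the change is worth making because it is cheap.

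**What to change.** Before database lock, state in A3 and in SAP 5.7.2.2 that the A3 imputed AE start date is not used for dose at onset. For dose at onset, take all dates compatible with the recorded partial date, bounded by first dosing and by the AE end date where these apply. If one dose category of the tables was in force throughout that interval, assign it. Otherwise count the event in a row for dose at onset not determinable, still included under all palovarotene.

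The cost is two sentences and one table row, with no new data. The downside is that a few events will sit in that row; their number will also show how much partial dating matters.

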#### *Algorithm for Prior/ Concomitant*

In case of partial start and/or stop medication/ non-drug therapies/surgical procedures dates, imputation will be done to determine the classification:

- If a partial start date, the first day of the month will be imputed for missing day and January for missing month,
- If a partial stop date, the last day of the month will be imputed for missing days and December will be imputed for missing month.

In case incomplete start or stop date does not allow the classification, it will be classified as concomitant.

#### *Algorithm for TEAE*

The date imputation algorithm for incomplete adverse event start dates is described in the table below. Classification of adverse event according to its treatment-emergent status is then done using the imputed date.

In the following table, all dates are presented using an YYYY-MM-DD format. As an example, suppose First IMP administration = 2002-08-11 and several AEs have incomplete start dates.

Description of incomplete date	Imputed numeric date	Example	
		Character date	Imputed date
Day is missing			
YYYY-MM < YYYY-MM of [First IMP admin.]	YYYY-MM-01	2002-07-XX	2002-07-01
YYYY-MM = YYYY-MM of [First IMP admin.]	Min ([First IMP admin.], AE end date)	2002-08-XX	Min (2002-08-11, AE end date)
YYYY-MM > YYYY-MM of [First IMP admin.]	YYYY-MM-01	2002-09-XX	2002-09-01
Day and month are missing			
YYYY < YYYY OF [First IMP admin.]	YYYY-01-01	2001-XX-XX	2001-01-01
YYYY = YYYY OF [First IMP admin.]	Min ([First IMP admin.], AE end date)	2002-XX-XX	Min (2002-08-11, AE end date)

YYYY > YYYY OF [First IMP admin.]	YYYY-01-01	2003-XX-XX	2003-01-01
Day, month, and year are missing			
XXXX-XX-XX	Min ([First IMP admin.], AE end date)		Min (2002-08-11, AE end date)

YYYY = non-missing year, MM = non-missing month, DD = non-missing day, XX = missing field.

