8.3.1 Time Period and Frequency for Collecting AE and SAE Information

All AEs (including SAEs) will be collected from the signing of the ICF until last study intervention intake + 30 days at the time points specified in the SoA (Table 1).

All AEs that first occurred during participation in the parent study and are ongoing at the time of transition to Study CLIN-60120-452 will be collected and entered again as ongoing AEs/SAEs in the Study CLIN-60120-452 eCRF at the signing of the ICF.

All SAEs will be recorded and reported to the sponsor or designee immediately and under no circumstance should this exceed 24 hours of awareness of the event, as indicated in Section 10.3. The investigator will submit any updated SAE data to the sponsor within 24 hours of it being available.

Investigators are not obligated to actively seek information on AEs or SAEs after conclusion of the study participation (unless any AEs/SAEs or their sequelae persist after this date, follow-up is required until the event or its sequelae resolve or stabilise, or the participant is lost to follow-up). However, if the investigator learns of any SAE, at any time after a participant has been discharged from the study, and he/she considers the event to be reasonably related to the study intervention or study participation, the investigator must promptly notify the sponsor (through pharmacovigilance).

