9.4.2 Analysis of Primary Endpoint

The primary endpoint is the incidence and description of all TEAEs, serious and nonserious treatment-related TEAEs, all serious TEAEs and all nonserious TEAEs.

A TEAE is defined as any AE that occurs after signing the ICF of Study CLIN-60120-452 or an ongoing AE from the parent study with a worsening in severity or relationship to the study intervention following transition to Study CLIN-60120-452.

Ongoing AEs from the parent study with no change in severity or relationship to the study intervention following transition to Study CLIN-60120-452 will not be considered TEAEs.

Any event that first occurred during participation in the parent study and is ongoing at the time of transition to Study CLIN-60120-452 will therefore be a (non-TEAE) AE.

All ongoing AEs from the parent study and all TEAEs that occur following the signing of the ICF until last study intervention intake + 30 days will be included in the participant data listings using the Full Analysis Set (FAS)/Safety Set. Primary endpoint analyses and summary tables will be presented by parent study, by palovarotene status at the time of transition to Study CLIN-60120-452 and treatment regimen and overall for the FAS/Safety Set.

Adverse events/TEAEs will be coded according to Medical Dictionary for Regulatory Activities (MedDRA) and will be classified by PT and SOC. Adverse events/TEAE listings will be presented by participant, SOC and PT.

The incidence of all reported TEAEs, serious and nonserious treatment-related TEAEs, all serious TEAEs, all nonserious TEAEs, TEAEs leading to death and TEAEs leading to treatment discontinuation will be tabulated separately. In addition, summary tables for TEAEs will be presented by maximum intensity and study intervention relationship (investigator-reported causality assessment).

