### 5.7.2.2 Primary Analysis – Adverse Events

All adverse events (AEs) recorded in the eCRF will be coded using the latest version of MedDRA dictionary at the time of the database lock and will be classified by System Organ Class (SOC) and Preferred Term (PT). [Note: All ongoing AEs at the time of participant transition will be transferred from the parent study database]

AEs will be classified as Treatment-Emergent AEs (TEAEs) according to the rules below:

- Events with start date on or after the date of first IMP administration and up to 30 days after date of last dose of treatment of palovarotene in Study CLIN-60120-452 (or date of last contact if not available).

- Ongoing AEs from the parent study with a worsening in intensity or relationship (see relationship and intensity order below) to the study intervention following transition to Study CLIN-60120-452. New AEs during Study CLIN-60120-452 will be compared by SOC and PT to all previous study ongoing AEs for comparison of the intensity and relationship.

Ongoing AEs from the parent study with no change in intensity or relationship to the study intervention following transition to Study CLIN-60120-452 will therefore be an AE (non-TEAE).

In the case where it is not possible to define an AE as treatment emergent or not, the AE will be classified by the most conservative case; i.e. treatment emergent.

The below summaries will be provided:

- An overview table summarising the:
  - number and percentage of participants with at least one of the following AEs: any AE; any TEAE; maximum intensity of TEAEs; causality of TEAEs, worst causality and intensity of TEAEs (worst case); TEAE leading to a dose change; TEAE leading to withdrawal; TEAE leading to death; Serious Adverse Events (SAEs); Serious TEAE;
  - corresponding number of events for each of the AE categories listed above
- A summary of the number and percentage of participants reporting an AE by SOC and PT
- A summary of the number and percentage of participants reporting a TEAE by SOC and PT
- A summary of the number and percentage of participants reporting a TEAE by maximum intensity, SOC and PT
- A summary of the number and percentage of participants reporting a TEAE by worst causality, SOC and PT
- A summary of the number and percentage of participants reporting a related TEAE by SOC and PT
- A summary of the number and percentage of participants reporting a TEAE by intensity, causality, SOC and PT

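### SAP Appendix A3 can date an unchanged parent-study AE to first dose and count it as a TEAE, against the plan's own origin rule, because no precedence is stated

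*SAP*

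**What the plan says.** **Rule by origin.** Protocol 9.4.2 takes these events out of the TEAE definition: "Ongoing AEs from the parent study with no change in severity or relationship to the study intervention" following transition are not TEAEs. SAP 5.7.2.2 repeats the rule with intensity in place of severity.

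**Rule by date.** The first TEAE criterion in SAP 5.7.2.2 is "Events with start date on or after the date of first IMP administration and up to 30 days after date of last dose". It makes no exclusion for parent-study events. Appendix A3 supplies the date when the recorded one is incomplete. If the known part matches the month or year of first dose, or nothing is known, the start becomes "Min ([First IMP admin.], AE end date"), that is, the earlier of the two dates. A3 then says: "Classification of adverse event according to its treatment-emergent status is then done using the imputed date". The general paragraph of A3 presumes onset on treatment "except if the partial onset date or the stop date indicates differently". Parent origin is not among the exceptions.

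**Fallback.** Where status cannot be determined, SAP 5.7.2.2 defaults to treatment-emergent.

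**Source of the records.** A note in SAP 5.7.2.2 reads: "All ongoing AEs at the time of participant transition will be transferred from the parent study database". Protocol 8.3.1 says that the same events "will be collected and entered again as ongoing AEs/SAEs in the Study CLIN-60120-452 eCRF at the signing of the ICF". Footnote s of the schedule (in both documents) and the AE row of that table agree with Protocol 8.3.1.

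**The concern.** The incidence and description of TEAEs is the primary endpoint. In a rollover study, AEs that cross the transition are expected, and some may carry incomplete start dates. For such a record the plan gives two instructions that can produce opposite answers. A programmer who codes A3 as written overrides the origin rule, although the record itself shows that the event began before this study. For an unchanged parent AE the error can only add TEAEs. Each such event would then also enter the TEAE tables by intensity, causality and dose at onset.

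The disagreement about where these AEs come from is a smaller, related matter. If both sources were loaded, the same AE could be counted twice in the all-AE event numbers of the overview table, and no de-duplication rule is given.

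**Working it through.** **Inputs.** The A3 imputation table and its example, with first dose on 2002-08-11; the date criterion in SAP 5.7.2.2 (start on or after first dose); the origin rule in SAP 5.7.2.2 and Protocol 9.4.2; the maximum of 87 participants (SAP 2.3).

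**Step 1: reproduce A3 and apply the date criterion.** For an AE with no end date, the earlier of first dose and end date is first dose. All seven of A3's example patterns reproduce:

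| Recorded start | A3 date | TEAE by date? | Possible for a parent AE? |
|---|---|---|---|
| 2002-07-XX | 2002-07-01 | No | Yes |
| 2002-08-XX | 2002-08-11 | **Yes** | **Yes** |
| 2002-09-XX | 2002-09-01 | Yes | No, onset after first dose |
| 2001-XX-XX | 2001-01-01 | No | Yes |
| 2002-XX-XX | 2002-08-11 | **Yes** | **Yes** |
| 2003-XX-XX | 2003-01-01 | Yes | No, onset after first dose |
| Wholly missing | 2002-08-11 | **Yes** | **Yes** |

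So three patterns turn a carried-over AE into a TEAE. A parent AE that resolves after first dose behaves in the same way, because the earlier of first dose and a later end date is first dose. One that ended before first dose (for example 2002-08-05) keeps its end date as the imputed start and stays non-emergent. In the example, the true onset behind 2002-08-XX could be any of the 10 days from 1 to 10 August. Behind 2002-XX-XX it could be any of the 222 days from 1 January to 10 August.

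**Step 2: apply the origin rule first.** If an unchanged parent AE is set to non-TEAE before any date is imputed, all three patterns give non-TEAE. The order of the two rules alone decides the result.

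**Step 3: how often an incomplete date would matter.** The documents do not say how many parent AEs have incomplete dates. As an illustration only, assume that onset is uniform over the 365 days before a first dose on 15 January, 15 June or 15 December 2022. The share of incompletely dated events moved to TEAE is then:

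- Day missing: 14/365 = 3.8% for each of the three dates.
- Day and month missing: 14/365 = 3.8%, 165/365 = 45.2% and 348/365 = 95.3%.
- Wholly missing: 100%.

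Over 730 days the same counts give 1.9% for a missing day; 1.9%, 22.6% and 47.7% for missing day and month; and again 100% for a wholly missing date. These are shares of incompletely dated events, not of all carried-over AEs.

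**Step 4: effect on the primary summary.** One participant whose only TEAE arises this way adds 1/87 = 1.15 percentage points to overall incidence; five add 5/87 = 5.75 points. Because participants are counted once per preferred term, the same 1.15 points applies to a preferred-term row when the participant has no other TEAE under that term. As 87 is the maximum enrolment, 1.15 is the smallest value the step can take; it is larger in the columns by treatment regimen.

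**The case against.** The best defence is that SAP 5.7.2.2 is the primary-analysis section and deals with parent AEs by name, while A3 is a general convention, so the specific rule should govern. The default to treatment-emergent applies only when status cannot be determined, and a known, unchanged parent AE can be determined. A3's conservative direction is declared, nothing is tested, and all AEs are listed with an emergence flag and with dates as recorded, so affected records can be traced.

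Much of this stands, and it limits the consequence. It does not settle the order of the rules: A3 says outright that status follows from the imputed date, and its exceptions do not mention parent origin.

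Four stronger readings are tempting, but the documents do not support them:

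- *The SAP ignores parent origin.* Only the A3 table does; SAP 5.7.2.2 has an origin rule.
- *Two sources would double the TEAE counts.* A duplicate with a complete pre-study date is non-TEAE in both copies, and participants are counted once per term. Only the all-AE event numbers would rise. SAP 5.1.3 also uses the idea of transfer to cover entry by the site, so the note in 5.7.2.2 may be loose wording; nothing plans to stack two AE datasets.
- *Matching on SOC and PT creates false TEAEs.* The SAP says "New AEs during Study CLIN-60120-452 will be compared by SOC and PT to all previous study ongoing AEs". A new AE starting on or after first dose, within the treatment-emergent window, is already a TEAE whatever it matches. Reading a re-keyed intensity as worsening would require treating a re-entered ongoing AE as new, which Protocol 8.3.1 and footnote s do not do.
- *The effect is large because skin reactions reached 98.8%.* That figure, in Protocol 2.2.3, describes reactions reported during earlier studies, not AEs still ongoing at transition. Protocol Table 2 calls mucocutaneous effects generally reversible.

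**Conclusion.** The point holds as a conflict between two stated rules with no order of precedence, affecting the primary endpoint. It reaches only parent AEs that are ongoing at transition, have not ended before first dose, and have a start date incomplete in one of three ways. Within that group, a literal reading of A3 classifies an unchanged event wrongly every time, and always towards TEAE.

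The total effect cannot be computed, because the documents give neither the number of carried-over AEs nor the share with incomplete dates. The firm figure is 1.15 points per participant whose only TEAE arises this way, assuming all 87 are enrolled and treated. The percentages in Step 3 rest on assumed onset patterns and show only that the route ranges from rare to near-certain depending on how much of the date is missing.

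The wording on the source of these AEs should be reconciled, but as a separate and lesser matter: it bears on all-AE event numbers and does not by itself create TEAEs.

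**What to change.** 1. In SAP 5.7.2.2 and Appendix A3, state that parent origin is evaluated before date imputation. An AE recorded as ongoing from the parent study can become a TEAE only through a recorded worsening of intensity or of relationship to study drug; an imputed start date cannot make it one.
2. Correct the note in SAP 5.7.2.2 to name the site re-entry in the CLIN-60120-452 eCRF (Protocol 8.3.1, schedule footnote s) as the single source for these AEs. Use the parent database only for reconciliation, so that no AE is counted twice in the all-AE event numbers.

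The first change needs each re-entered record to be identifiable as a parent AE. The documents do not describe an eCRF field for this; if there is none, the reconciliation can supply it. The cost is SAP wording and minor programming. SAP Section 1 foresees finalisation before database lock, so the change belongs there; after lock it would have to be documented in the CSR as a deviation.
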